6.3.6. Change from Baseline to Week 24 in SLEDAI-2K Score (Part A Only)

The change from baseline to each post-baseline week in the SLEDAI -2K score will be analyzed as described for continuous endpoint analysis in [Section 6.1.1](#).

6.3.7. Proportion of Subjects with No New BILAG-2004 A and no More than One New BILAG-2004 B at Week 24 (Part A Only)

The proportion of subjects who had no new BILAG-2004 A and no more than one new BILAG-2004 B from baseline to Week 24 will be analyzed as described for binary endpoint analysis in [Section 6.1.1](#).

6.3.8. Change from Baseline to Week 24 in PGA of SLE (VAS) Score (Part A Only)

The change from baseline to week 24 in the PGA of SLE (VAS) score will be analyzed as described for continuous endpoint analysis in [Section 6.1.1](#).

CONFIDENTIAL

The information contained herein may not be used, disclosed, or published without the written consent of Biogen MA Inc.

Black box

CONFIDENTIAL

The information contained herein may not be used, disclosed, or published without the written consent of Biogen MA Inc.

CONFIDENTIAL

The information contained herein may not be used, disclosed, or published without the written consent of Biogen MA Inc.

CONFIDENTIAL

The information contained herein may not be used, disclosed, or published without the written consent of Biogen MA Inc.

CONFIDENTIAL

The information contained herein may not be used, disclosed, or published without the written consent of Biogen MA Inc.

CONFIDENTIAL

[figure not shown]
[figure not shown]
[figure not shown]
The information contained herein may not be used, disclosed, or published without the written consent of Biogen MA Inc.

CONFIDENTIAL

The information contained herein may not be used, disclosed, or published without the written consent of Biogen MA Inc.

- [REDACTED]
- [REDACTED]

For more information, contact the Office of the Vice President for Research and Economic Development at [contact] or [contact].

- 
- 
- 
- 
- 
- 
- 
- 
- 
- 
- 
- 
- 
- 
- 
- 
- 
- 
- 
- 
- 
- 
- 
- 

CONFIDENTIAL

The information contained herein may not be used, disclosed, or published without the written consent of Biogen MA Inc.

 Biogen	Statistical Analysis Plan 230LE201	<V 2.0>
--	---	----------------------

- [REDACTED]
- [REDACTED]
- [REDACTED]

6.5. Multiplicity Adjustment

Part A

There will be no adjustment for multiplicity at interim or final analysis for the primary or secondary endpoints in Part A.

Part B

Multiple Comparison Procedure-Modeling (MCP-Mod) methodology ([Bretz et al. 2005](#)) will be used to test the dose-response relationship across 3 doses of BIIB059 and PBO for the percent change from baseline in CLASI-A score at interim and final analysis. Five dose-response trends will be tested using the optimal contrasts as determined by the MCP-Mod methodology such that the overall Type I error rate is controlled at 0.05 (one-sided testing).

There will be no adjustment for multiplicity with secondary efficacy endpoints at interim or final analysis.

6.6. Handling of Missing Data

The handling of missing data and data from treatment failure subjects is summarized here and applies to all the endpoints unless otherwise specified. For composite endpoints (e.g.: SRI-4), the missing values will be imputed at each component endpoint level, as applicable, using the rules described below.

CONFIDENTIAL

The information contained herein may not be used, disclosed, or published without the written consent of Biogen MA Inc.

 Biogen	Statistical Analysis Plan 230LE201	<V 2.0>
--	---	----------------------

6.6.1. Continuous Endpoints

The primary approach described below will apply to both part A and part B continuous endpoints, unless otherwise specified. The sensitivity approach will be applied to the primary endpoints.

Primary approach

For subjects who are considered as treatment failures, as defined in [Section 5.8](#), the worse observation of the baseline and the last observation before treatment failure carried forward will be used as the primary method to impute values for all the visits post treatment failure visit. Under this approach, subject's post treatment failure data will be censored and then imputed with the subject's worst case non-missing data prior to treatment failure.

Data after treatment discontinuation will be censored and treated as missing data. For all other monotone and non-monotone missing data, including missingness post treatment discontinuation, mixed-effects model repeated measures (MMRM) model based approach will be used as the primary approach. MMRM assumes data is missing at random (MAR).

A few subjects from PV1 part B might have completed treatment up to week 12 but could not reconsent to PV2 and therefore will have missing week 16 data. These subjects will have week 16 data imputed using predicted value from the MMRM model.

Sensitivity analyses approach

For subjects who are considered as treatment failures, as defined in [Section 5.8](#), the worse observation of the baseline and the last observation before treatment failure carried forward will be used to impute values for all the visits post treatment failure visit. Under this approach, subject's post treatment failure data will be censored and then imputed with the subject's worse case between the baseline and the last non-missing data prior to treatment failure.

CONFIDENTIAL

The information contained herein may not be used, disclosed, or published without the written consent of Biogen MA Inc.

 Biogen	Statistical Analysis Plan 230LE201	<V 2.0>
--	---	----------------------

For all the other missing data, including missingness post treatment discontinuation, reference-based Multiple Imputation (MI) approach will be used to consider a missing not at random (MNAR) mechanism for monotonic missing data. Imputed values of subjects in the BIIB059 group will be based on the Placebo group. This approach assumes no sustained benefit of BIIB059 after discontinuation of study treatment and limits post-discontinuation effects to that of placebo.

Intermittent (non-monotonic) missing data will be imputed based on the MAR assumption and with an imputation model using Markov chain Monte Carlo (MCMC) method within each treatment group. The imputation models will include baseline value and the values at each post-baseline week for endpoint of interest. The MCMC method in the MI procedure in SAS will be used with a single chain, with a burn-in of 1000, and a thinning of 100 and non-informative priors for all parameters.

The remaining, monotonic missing data for all subjects who discontinue study treatment early will be imputed using sequential regression MI model estimated based on data from the placebo group only. Each sequential regression model (i.e., for imputation of values at a given week) will include terms for baseline score, the stratification factors, and all the continuous endpoint scores. Missing values at a given week in placebo and BIIB059 groups will be imputed from the same imputation model. No rounding or range restrictions will be applied to imputed continuous values.

200 imputations will be performed. Each of the 200 imputed datasets will be analyzed using the following method.

Results from analysis of each imputed dataset, i.e., least square (LS) mean differences from placebo and their SEs, will be combined using Rubin's method [\[Rubin 1987\]](#) as implemented in the SAS MIANALYZE procedure to produce a pooled LS mean estimate of treatment difference, its 95% CI, and a pooled p-value. A p-value will only be presented for the primary

CONFIDENTIAL

The information contained herein may not be used, disclosed, or published without the written consent of Biogen MA Inc.

comparison at primary timepoint. The LS means of change from baseline to each post-baseline week will be plotted by treatment group.

A figure of the change from baseline to the primary timepoint will be presented; for data imputed using the MI methodology described above the least square mean of the 200 imputed values will be used.

A few subjects from PV1 part B might have completed treatment up to week 12 but could not reconsent to PV2 and therefore will have missing week 16 data. These subjects' week 16 data will be considered MAR and imputed using MMRM.

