This statistical analysis plan covers the planned analyses for both the unblinded IA and the final analyses (Part A and Part B). All efficacy, safety and PK endpoints described in this plan will be included in the final analyses, while a subset of the endpoints will be included in the unblinded IA (see [Appendix B](#) for more details). For each endpoint, the same analysis method will be used for both the interim and final analyses, unless otherwise specified.

Within each part (Part A and Part B), all data will be summarized by treatment group. In addition for each part (Part A and Part B), the data described in [Section 5](#) which includes patient disposition, baseline characteristics and demography data, and concomitant medications will be summarized overall, and the safety data described in [Section 7](#) will also be summarized for all BIIB059 groups combined.

A pooled analysis (pooled data from Part A and Part B) may also be performed on Part B endpoints associated with CLASI-A assessment. Only the data from Part A subjects that meet the following criteria will be pooled (by treatment group) for the combined (Part A and Part B) analyses:

- Baseline CLASI-A ≥ 8

The pooled analyses will be performed using the same analysis method as for the CLASI-A endpoints within Part B, where applicable.

The statistical software, SAS® version 9.3 or above, will be used for all summaries and analyses.

CONFIDENTIAL

The information contained herein may not be used, disclosed, or published without the written consent of Biogen MA Inc.

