6.2.2. Sensitivity Analysis

A sensitivity analysis will be performed on both part A and part B primary endpoints using the same methods as described in [Section 6.2.1](#) but using a different missing data handling approach, reference based multiple imputation, as described in [Section 6.6](#).

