10.2. Interim Analysis 2 (IA2): End of Treatment Periods

After the last subjects complete the Double-Blind Treatment Periods for Part A (at Week 24) and Part B (at Week 16), an interim database lock will occur and an IA of efficacy and safety data will be conducted. All Investigators, study site personnel, and subjects will remain blinded to treatment assignments until after the end of the study. Members of the Biogen study team not in direct contact with the study sites will have access to the study data after all subjects complete all Week 24 assessments in Part A and all Week 16 assessments in Part B. Members of the Biogen study team who become unblinded to the data for this IA will have no further contact with study sites until after the final database lock.

Unblinding details will be provided in the unblinding plan.

The endpoints and analysis to be included in the IA1 and IA2 are listed in [Appendix B](#).

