Appendix B: Summary of Additional Interim Analyses

	Section of the SAP	Note:	Study Part
Subject disposition	5.2	IA1 and IA2, MITT population	Part A and B
Demography and baseline disease characteristics	5.3	IA1 and IA2, MITT population	Part A and B
Previous medications used for the treatment of SLE and/or CLE	5.4	IA1 and IA2	Part A and B
Treatment exposure	5.5	IA1 and IA2	Part A and B
Concomitant therapies	5.6	IA1 and IA2	Part A and B
Protocol Deviations	5.7	IA2: Summary of major protocol deviations	Part A and B
Primary endpoint: Primary analysis	6.2	IA1 and IA2: Part B: Model based and summary statistics over time Part A, IA1 Descriptive statistics by visit; IA2: Model based and summary statistics over time.	Part A and B
Secondary and additional efficacy endpoints	6.3, 6.4	Part A, IA1: Descriptive statistics by visit of the following endpoints- SRI-4, TJC, SJC, PGA of SLE (VAS), SLEDAI-2K, BILAG-2004, CLASI-A based endpoints, [REDACTED] [REDACTED] Part A, IA2: Model based and summary statistics by visit of the following endpoints- SRI-4, TJC, SJC, PGA of	Part A

CONFIDENTIAL

The information contained herein may not be used, disclosed, or published without the written consent of Biogen MA Inc.

		SLE (VAS), SLEDAI-2K, proportion of subjects with no new organ system affected, CLASI-A based endpoints, BILAG based severe flare; Descriptive statistics by visit for the following endpoints- BILAG-2004 score, [REDACTED] [REDACTED] [REDACTED]	
Secondary and additional efficacy endpoints	6.3, 6.4	Part B, IA1: Model based and summary statistic over time- CLASI-A based endpoints; Descriptive statistics by visit of the following endpoints- SLEDAI-2K, [REDACTED], Physicians Global assessment of SLE (VAS), [REDACTED]. Part B, IA2: Model based and summary statistic over time - CLASI-A based endpoints, SLEDAI-2K; Descriptive statistics by visit of the following endpoints - [REDACTED], PGA of SLE (VAS), [REDACTED] [REDACTED] [REDACTED]	Part B
Immunoglobulins (IgG, IgA, IgM) change from baseline by visit	7.3.2	Part A and B, IA1: Descriptive statistics by visit.	Part A and B

CONFIDENTIAL

The information contained herein may not be used, disclosed, or published without the written consent of Biogen MA Inc.

CONFIDENTIAL

The information contained herein may not be used, disclosed, or published without the written consent of Biogen MA Inc.

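### Does the loose paraphrase in SAP 6.6.1 create a second, conflicting imputation rule for treatment failures?

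*SAP*

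**What the plan says.** SAP 6.6.1 defines how continuous endpoints are handled after treatment failure, and its scope is wide: "The primary approach described below will apply to both part A and part B continuous endpoints, unless otherwise specified". It therefore supplies Week 24 joint counts in Part A and Week 16 CLASI-A scores in Part B for subjects who fail earlier.

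The primary approach takes two sentences. The first gives the rule, which it names as the primary method: "the worse observation of the baseline and the last observation before treatment failure carried forward" is used for all visits after the failure. The second, which opens by referring back to that approach, says post-failure data are censored and then imputed with the subject's "worst case non-missing data prior to treatment failure".

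The sensitivity approach repeats the first sentence almost unchanged, but its own restatement keeps the limit to two values: "worse case between the baseline and the last non-missing data prior to treatment failure".

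SAP 6.2.2 says the sensitivity analysis uses the methods of the primary analysis but "using a different missing data handling approach, reference based multiple imputation". Protocol 16.1.2.1 calls the method worst observation carried forward, applies it to the last post-baseline joint count before failure, and leaves details to the SAP.

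**The concern.** The first sentence compares two values. The second uses a superlative and names no candidates, so on its own it could mean the maximum over every earlier non-missing value. That is a different and harsher rule. The protocol's label, worst observation carried forward, could encourage that reading, and a programmer might take the contrast with the sensitivity paragraph as deliberate.

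The rule feeds both primary endpoints. Under the literal reading, the primary and sensitivity analyses would also differ in how they treat failures, whereas SAP 6.2.2 describes only a difference in missing-data handling.

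Timing adds some weight. Appendix B lists the primary endpoint for the second interim analysis in Part A as "IA2: Model based and summary statistics over time", and gives model-based results for Part B as well. SAP 10.2 says "Members of the Biogen study team not in direct contact with the study sites will have access to the study data" at that point, and SAP 3.1 says "the same analysis method will be used for both the interim and final analyses, unless otherwise specified". If the rule really were open, choosing a reading after that lock would be a post hoc choice about the primary endpoint.

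**Working it through.** No figure in the plan depends on this phrase. The sample-size sections assume 20% dropout but give no treatment-failure rate, so there is nothing to reproduce. The check is of the text, then of what a misreading would cost.

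**1. The two readings as formulas (higher is worse).**

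- Two-value rule: imputed value = max(baseline, last value before failure).
- Literal phrase: imputed value = max(all non-missing values before failure).

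| Baseline; later values before failure | Two-value rule | Literal phrase |
|---|---|---|
| 14; 12, 10, 8 | max(14, 8) = 14, change 0 | 14, change 0 |
| 14; 15, 16, 18 | max(14, 18) = 18, change +4 | 18, change +4 |
| 14; 12, 16, 15 | max(14, 15) = 15, change +1 | 16, change +2 |
| 14; 18, 15, 10 | max(14, 10) = 14, change 0 | 18, change +4 (4/14 = 28.6%) |

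The readings part only when some value other than baseline and the last observation is worse than both. Usually that is an intermediate visit. Taken fully literally, it could also be Screening, because joint counts are taken at Screening and Day 1 (Protocol Table 1). A Screening count of 18, baseline 14 and a single later value of 12 would give 0 against +4. The literal reading would then bring back a pre-treatment value that SAP 4.3 sets aside when it defines baseline as the last non-missing value before first dose. So the phrase needs its context to be workable, and that context also supplies the two-value limit.

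**2. Which reading the documents support.**

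- The first sentence is complete and is the one called the primary method.
- The second sentence presents itself as a description of that method.
- The sensitivity paragraph starts from the same rule and restates it with both values named.
- SAP 6.2.2 is accurate only if both analyses treat failures alike, as they do under the two-value rule.
- SAP 5.8 sends treatment-failure data to Section 6.6. Its addendum concerns concomitant-therapy definitions.
- Protocol 16.1.2.1 works from the last post-baseline value.

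No full statement of a rule in either document takes the worst of all earlier visits.

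**3. Cost if the phrase were programmed literally.** The simulation used 200,000 subjects per arm and 64 scenarios per part.

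- From the plan: SD 6 and difference 2.5 joints (Part A); SD 30 and difference 27.5 points (Part B).
- Assumed: failure rates of 10% to 30%; failure time uniform from first dose to the final visit; failure either independent of the last value or likelier when it is poor; AR(1) correlation 0.5 or 0.8; SD constant or growing with time; mean placebo change of -4 or -7 joints, or -10 or -25 points; Part B visits at Weeks 4, 8, 12 and 16.

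Standard errors after 20% dropout:

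- Part A: 50 × 0.8 = 40 per arm; 6 × √(2/40) = 1.34 joints.
- Part B: 25 × 0.8 = 20 per arm; 30 × √(2/20) = 9.49 points.

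| Shift in treatment difference | Equal failure rates | Placebo fails 10 points more often |
|---|---|---|
| Part A | -0.003 to 0.055 joints | 0.096 to 0.246 joints |
| Part B | 0.03 to 0.37 points | 0.22 to 0.62 points |

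The largest shifts are 0.246/1.34 = 0.18 and 0.62/9.49 = 0.07 standard errors. A separate coding gave 0.04 to 0.25 joints and 0.06 to 0.56 points for the unequal-rate case.

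**The case for a change.** The strongest case for acting is that likely intent does not make a sentence correct. The rule generates primary-endpoint values, the literal reading can be programmed, the protocol's label points the same way, and copying a phrase from the sensitivity paragraph would cost almost nothing before sponsor staff see unblinded data.

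The textual observation stands: the sentence is looser than its counterpart, and the two functions do differ. The rest is weaker. The protocol's label is followed at once by a reference to the last post-baseline count, which goes against the literal reading. The post hoc worry needs an open choice. Because the preceding sentence already fixes the rule, correcting a literal programme would bring it into line with the SAP, before or after the lock. Nothing in the documents suggests a literal programme exists.

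The simulated shifts do not strengthen the case. They depend on assumed failure rates and timing. The share of failures affected ranges from 30% to 47% under the Part A assumptions above, but from 21% to 72% in a simpler model that fixes two to five post-baseline visits before failure. The Part B figures describe one dose against placebo, whereas the primary test is the MCP-Mod dose-response test. They also omit Week 2, which the SAP model lists. Both standard errors use only the 100 planned subjects per part, although SAP 3.1 pools data from protocol version 1.

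**Conclusion.** This is a clerical slip. SAP 6.6.1 fixes the treatment-failure rule as the worse of baseline and the last observation before failure, and both its primary and sensitivity paragraphs support that reading. Followed as written, the section gives one imputed value per failure and the same failure handling in both analyses. A tidier second sentence would change no imputed value, estimate or p-value.

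This conclusion assumes only that the analyst reads the two sentences together. If that failed, the shift would be at most about 0.18 standard errors in Part A and 0.07 in Part B, and those figures need placebo to fail 10 percentage points more often. They are illustrations under assumed inputs, not estimates for this trial. No change to the plan follows.

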6. EFFICACY ANALYSES

6.1. General Considerations

For both Part A and Part B, the efficacy analyses will be performed using the MITT population and will be considered as the primary analyses. For each endpoint, additional conditions may apply for pooling of data across protocol versions (see [Section 3.1](#)). The final model for each analysis in the MITT population will also be used for the PP analysis. A complete list of all the planned analyses and target population for the primary and secondary endpoints is provided in [Appendix A1](#) (Part A) and [Appendix A2](#) (Part B).

Unless otherwise specified, statistical testing across all efficacy endpoint will be performed to compare each BIIB059 dose (Part A: 450 mg; Part B: 50, 150 or 450 mg) with placebo at the 2-sided, 0.05 significance level. P-values and corresponding 95% confidence intervals (CI) will be provided. P-values will be rounded to three decimal points before assessing statistical significance.

CONFIDENTIAL

The information contained herein may not be used, disclosed, or published without the written consent of Biogen MA Inc.

 Biogen	Statistical Analysis Plan 230LE201	<V 2.0>
--	---	----------------------

Summary statistics will be presented for all endpoints at all visits including follow-up visits. For continuous variables, the summary statistics will include number of subjects with data, mean, standard deviation (SD), median, first quartile (Q1), third quartile (Q3), minimum and maximum. For categorical endpoints, the summary statistics will generally include: number of subjects in the corresponding analysis population, number and percentage of subjects in each category.

Unless otherwise specified, week 2, 4, 8, 12, 16, 20 and, 24 will be included in all Part A “by visit” MMRM analyses.

Unless otherwise specified, week 2, 4, 8, 12 and, 16 will included in all Part B “by visit” MMRM analyses.

Additional study part specific efficacy analyses considerations are described in [Section 6.1.1](#) (Part A) and [Section 6.1.2](#) (Part B)

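### The sensitivity imputation is described as allowing no benefit after stopping BIIB059, but for discontinuations that are not treatment failures it carries some, and possibly most, of the on-drug benefit forward

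*SAP*

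**What the plan says.** SAP 6.2.2 plans one sensitivity analysis for both primary endpoints, "using a different missing data handling approach, reference based multiple imputation". SAP 6.6.1 gives the details.

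- **Purpose.** It is a missing-not-at-random alternative to the MMRM, for data missing after treatment discontinuation. Its stated property is: "This approach assumes no sustained benefit of BIIB059 after discontinuation of study treatment and limits post-discontinuation effects to that of placebo".
- **Model.** Monotone missing values are "imputed using sequential regression MI model estimated based on data from the placebo group only". Each regression "will include terms for baseline score, the stratification factors, and all the continuous endpoint scores".
- **Application.** "Missing values at a given week in placebo and BIIB059 groups will be imputed from the same imputation model".
- **Treatment failures.** These are handled separately: "the worse observation of the baseline and the last observation before treatment failure carried forward will be used to impute values". The primary approach uses the same rule.
- **Other gaps.** Intermittent missing values are imputed under missing at random within arm. Part B subjects from protocol version 1 who have no Week 16 visit are also treated as missing at random.

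**The concern.** The description and the model are a few lines apart and do not agree. A BIIB059 subject who stops at Week 8 has Week 2, 4 and 8 scores that already contain the drug effect. If those scores enter a regression with placebo coefficients, the prediction is the placebo mean plus a fraction of the advantage the subject had gained. That fraction is zero only if earlier scores do not predict later ones.

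This is the only sensitivity analysis the SAP designates for the two primary endpoints, and the readable text contains no jump-to-reference or tipping-point analysis. A report repeating the SAP's sentence would claim that the result survives complete loss of effect after stopping, when only part of that loss had been tested.

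**Working it through.** **Inputs.**
- Part B: effect 27.5 points at 450 mg, SD 30, 20% dropout. Part A: effect 2.5 joints, SD 6, 20% dropout. (Protocol 16.8, SAP 11.)
- Model visits (SAP 6.1): Weeks 2, 4, 8, 12, 16, 20, 24 in Part A; Weeks 2, 4, 8, 12, 16 in Part B.
- Within-subject correlation: not given. Assumed 0.3 to 0.9, either compound symmetry (CS) or first-order autoregressive by visit (AR1).
- Time course: not given. Assumed either flat from the first visit or rising linearly with week.
- Assumed also: discontinuers had the average drug effect, dropout is spread evenly over visits, and there are no treatment failures.
- The endpoint scores in each regression are read as this endpoint's scores at earlier visits, the natural reading of a sequential regression.

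**The plan's own figure.** The sensitivity analysis has none. The planning inputs do reproduce the stated Part A power: 40 completers per arm, difference 2.5, SD 6 and two-sided 0.2 (Protocol 16.8) give 0.72 by noncentral t, against 71% stated.

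**Reference values.** No benefit after stopping: 27.5 × 0.8 = 22.0 points; 2.5 × 0.8 = 2.0 joints. Full benefit under missing at random: 27.5 and 2.5.

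**Share carried forward.** Let V be the placebo covariance, T the primary visit, obs the baseline and observed visits, and δ the drug-placebo difference (zero at baseline). The expected imputed difference is V(T,obs) V(obs,obs)⁻¹ δ(obs). Dividing by δ(T) gives the share s. Closed forms:
- CS, flat, k post-baseline visits observed: s = kρ/(1 + kρ). Example: ρ = 0.9, k = 4 gives 3.6/4.6 = 0.78.
- AR1, flat, last score m visits before T: s = ρ^m. Example: ρ = 0.9, m = 1 gives 0.90.
- AR1, rising: s = ρ^m × (last week/final week). Example: ρ = 0.9, last score at Week 12 of 16 gives 0.9 × 0.75 = 0.68.

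**Estimate.** Effect × (0.8 + 0.2 × mean s). Part B, share of the Week 16 effect by last observed week (estimates use unrounded shares):

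| Benefit, correlation | Wk 2 | Wk 4 | Wk 8 | Wk 12 | Mean | Estimate |
|---|---|---|---|---|---|---|
| Flat, CS 0.3 | 23% | 38% | 47% | 55% | 41% | 24.2 |
| Flat, CS 0.9 | 47% | 64% | 73% | 78% | 66% | 25.6 |
| Flat, AR1 0.3 | 1% | 3% | 9% | 30% | 11% | 22.6 |
| Flat, AR1 0.9 | 66% | 73% | 81% | 90% | 77% | 26.3 |
| Rising, CS 0.3 | 3% | 7% | 14% | 22% | 11% | 22.6 |
| Rising, CS 0.9 | 6% | 12% | 21% | 32% | 18% | 23.0 |
| Rising, AR1 0.3 | 0% | 1% | 4% | 22% | 7% | 22.4 |
| Rising, AR1 0.9 | 8% | 18% | 41% | 68% | 34% | 23.8 |

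Part A, same method, mean share and estimate:
- Flat: CS 0.3, 48%, 2.24; CS 0.9, 72%, 2.36; AR1 0.3, 7%, 2.04; AR1 0.9, 70%, 2.35.
- Rising: CS 0.3, 13%, 2.07; CS 0.9, 19%, 2.09; AR1 0.3, 5%, 2.03; AR1 0.9, 34%, 2.17.

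The Part A maximum is 2.5 × (0.8 + 0.2 × 0.715) = 2.36.

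**Simulation check.** Running the specified procedure for Part B with flat benefit and CS 0.6 gave 25.1 points. The formula gives a mean share of 0.567, so 27.5 × (0.8 + 0.1134) = 25.1.

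**The case against.** The mismatch itself is hard to dispute. The objections concern its size and reach.

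- **Size.** A reader might infer that a large part of the benefit is always carried forward. The documents do not support that. They give neither a correlation nor a time course, and by dropout visit the share runs from near 0% to 90%. The high figures need a flat benefit, strong correlation and late dropout. The protocol's Version 2 amendment summary justifies the longer Part B with comparator data suggesting the CLASI response is still developing at Week 16, which favours a rising benefit. In the rising cases tabulated, the mean share is 7% to 34%. This objection stands.
- **Who drops out.** If discontinuers are poor responders, little is carried forward, because the model uses their own poor scores. The 27.5 points is also the maximal effect; a dose with a smaller effect shifts less. Both stand as limits on the size.
- **Treatment failures.** A reader might extend the point to all subjects who go off plan. That is wrong: failures receive the worse of baseline and last pre-failure value, so no improvement over baseline is carried. Because the primary analysis uses the same rule, however, it adds no further stress in the sensitivity analysis.
- **Retrieved-dropout analysis.** SAP 6.10 also analyses scores collected after stopping, which is useful context. The SAP itself says this addresses a different estimand and is not a sensitivity analysis of the primary endpoint, so it does not close the gap.
- **Primary result.** Nothing here suggests that the primary analysis is biased. In every case run the sensitivity estimate remains below the missing-at-random value, so the analysis does apply some penalty.

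**Conclusion.** The concern holds for monotone missing data after discontinuation in subjects who are not treatment failures. The SAP attributes to its sensitivity analysis a property that the specified model lacks whenever visits are positively correlated. The supportable wording is that some, and possibly most, of the benefit is carried forward, depending on correlation, time of discontinuation and time course.

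Under the assumptions listed, the Part B estimate exceeds the stated no-benefit value by about 0.4 to 4.3 points out of an intended reduction of 27.5 − 22.0 = 5.5. The Part A estimate exceeds it by about 0.03 to 0.36 joints out of 2.5 − 2.0 = 0.5. The direction does not depend on the assumed values, provided discontinuers had some benefit on drug; the size does. The correction is worth making because this is the only designated sensitivity analysis of either primary endpoint.

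**What to change.** Specify a jump-to-reference analysis for both primary endpoints, in which the BIIB059 mean after discontinuation is set to the placebo mean path. State one version only, because two are in use and they differ:
- keep each subject's deviation from the BIIB059 mean before stopping and add it, through the placebo regression, to the placebo mean; or
- impute from placebo given baseline and stratification factors alone, which discards the subject's history.

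Then either replace the current model or keep it as a second analysis. If it is kept, label it copy-reference, say that the benefit fades with the within-subject correlation, and remove the sentence claiming no sustained benefit. State in 6.6.1 that the analysis covers monotone missing data in subjects who are not treatment failures.

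The cost is SAP text and minor programming, with no new data and no change to trial conduct. The sensitivity estimate will probably be somewhat less favourable. That is not certain: under the second version, a BIIB059 subject who stops with scores worse than placebo would be imputed a better value than the current model gives.
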